## Apellis Pharmaceuticals, Inc. Protocol: APL2-CP-AIHA-208

Protocol: APL2-CP-AIHA-208 Part B Long Term Extension Statistical Analysis Plan

	Part B Visit 7 (Week 84)	Part B Study Day 588	Part B Study Day 546 - Part B Study Day < 630	84
Part A + B, cont.	Part B Visit 8 (Week 96)	Part B Study Day 672	Part B Study Day 630 - Part B Study Day < 714	84
	Part B Visit 9 (Week 108)	Part B Study Day 756	Part B Study Day 714 - Part B Study Day < 798	84
	Part B Visit 10 (Week 120)	Part B Study Day 840	Part B Study Day 798 - Part B Study Day < 882	84
	Part B Visit 11 (Week 132)	Part B Study Day 924	Part B Study Day 882 - Part B Study Day < 966	84
	Part B Visit 12 (Week 144)	Part B Study Day 1008	Part B Study Day 996 - Part B Study Day < 1050	84
	Part B Visit 13 (Week 156)	Part B Study Day 1092	Part B Study Day 1050 - Part B Study Day < 1134	84
	Part B Visit 14 (Week 168)	Part B Study Day 1176	Part B Study Day 1134 - Part B Study Day < 1218	84

Version 1.0

08 Nov 2022

\*For baseline assessments, must be prior to dosing.

Table 2: Visit Windowing For Part B

Part	Study Visit	Target Day	Analysis Window	Interval	
Part B	Part B Baseline (Day 1)	Date of First 1080 mg Dose = Part B Study Day 1	$\leq$ Part B Study Day 1*	NA	
	Part B Transition Visit 1 (Day 7)	Part B Study Day 7	> Part B Study Day 3 - < Part B Study Day 11	7	
	Part B Transition Visit 2 (Week 2)	Part B Study Day 14	Part B Study Day 11 - < Part B Study Day 21	10	
	Part B Transition Visit 3 (Week 4)	Part B Study Day 28	Part B Study Day 21 - < Part B Study Day 56	25	
	Part B Visit 1 (Week 12)	Part B Study Day 84	Part B Study Day 56 - Part B Study Day < 126	70	
	Part B Visit 2 (Week 24)	Part B Study Day 168	Part B Study Day 126 - Part B Study Day < 210	84	
	Part B Visit 3 (Week 36)	Part B Study Day 252	Part B Study Day 210 - Part B Study Day < 294	84	
	Part B Visit 4 (Week 48)	Part B Study Day 336	Part B Study Day 294 - Part B Study Day < 378	84	
	Part B Visit 5 (Week 60)	Part B Study Day 420	Part B Study Day 378 - Part B Study Day < 462	84	
	Part B Visit 6 (Week 72)	Part B Study Day 504	Part B Study Day 462 - Part B Study Day < 546	84	
	Part B Visit 7 (Week 84)	Part B Study Day 588	Part B Study Day 546 - Part B Study Day < 630	84	
	Part B Visit 8 (Week 96)	Part B Study Day 672	Part B Study Day 630 - Part B Study Day < 714	84	

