## 2. INTRODUCTION

This Statistical Analysis Plan (SAP) is prepared to provide a more technical and detailed elaboration of the principal statistical features stated in the protocol. The SAP will ensure that the tables, listings, and figures that will be produced and statistical methods that will be used for the final analysis are complete and accurate and will allow valid conclusions to be drawn.

In the development of this final analysis SAP, the following study documents were used:

- Protocol Number (Version 1.0 Amendment 4), 17 Jan 2019
- Electronic Case Report Form (eCRF), extracted 18 Oct 2021
- Medical Coding Guidelines (Version 5.0), 10 Sep 2021

The study protocol consists of two study parts for analysis (details of the scheduled assessments of the study parts can be found in Section 3.3 of the SAP):

- Core Study Phase (Part A): the study period of the daily 270/280 mg or 360 mg APL-2 dose regimen.
- Long Term Extension Phase (Part B): the study period of the twice or three times weekly 1080 mg APL-2 dose regimen.

Statistical Analysis Plan Version 1.0 was used for the production of the Interim Part A Core Study Phase Analysis. This SAP will present the results for the final analysis for subjects who rolled over into Part B, presenting the safety and efficacy results of Part B and Part A + B as whole completed study as well. Definitions for the study days and baselines are outlined in Section 4. Details of the planned analyses are outlined in Section 5.

In the event that a discrepancy is found between the descriptions in the statistical section of the protocol and this document, the description in this document supersedes the descriptions in the statistical section of the protocol. Any deviations from the final analysis plan or from what is outlined in the protocol will be discussed in the final study report.

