#### 4.2.3 Visit Windowing Based on Study Day

Data will be summarized and analyzed based on the list of visits specified in table below for Part A + B and the Part B. The relative day will be used to assign analysis visit following the table below. All the records post-baseline will be assigned to an appropriate analysis visit using the following:

For the post-baseline visits, the lower and the upper bound for the analysis visit windows are defined as the midpoints of the target date of the scheduled visits. If the date of assessment falls in between the lower bound and the upper bound for a visit as specified in the schedule of assessments of the protocol, then it will be assigned to that visit. If the interval separating 2 scheduled visits is an even number of days, the middle day will be included in the lower bound of the next visit. If more than 1 record is within the same analysis visit window, the record closest to the midpoint of the interval will be used in the analysis. If 2 records are tied before and after the middle of the interval, the earlier record will be used in the analysis. If more than one assessment (including the early termination or unscheduled assessments) falls within the same defined window, the assessment closest to the target day with non-missing data will be considered for analysis.

In listings that are presented by visit, windowed assessments that are used in the analysis tables by visit will be identified.

Part	Study Visit	Target Day	Analysis Window	Interval
Part A + B	Part A Visit 1 (Screening)	Part A+B Study Day -30	<1*	NA
	Part A Visit 2 (Baseline)	Part A+B Study Day 1	1*	1
	Part A Visit 3 (Day 2)	Part A+B Study Day 2	2	1
	Part A Visit 4 (Day 3)	Part A+B Study Day 3	3	1
	Part A Visit 5 (Day 7)	Part A+B Study Day 7	>=4-<11	7

Table 1: Visit Windowing for Part A + B Analyses

Apellis Pharmaceuticals, Inc.
-------------------------------

Part B Long Term Extension Statistical Analysis Plan   Version 1.0   08 Nov 2022					
	Part A Visit 6 (Week 2)	Part A+B Study Day 14	11-<21	10	
	Part A Visit 7 (Week 4)	Part A+B Study Day 28	21-<42	21	
	Part A Visit 8 (Week 8)	Part A+B Study Day 56	42 - <70	28	
	Part A Visit 9 (Week 12)	Part A+B Study Day 84	70 - < 98	28	
	Part A Visit 10 (Week 16)	Part A+B Study Day 112	98 - < 126	28	
Part A + B, cont.	Part A Visit 11 (Week 20)	Part A+B Study Day 140	126 - < 154	28	
	Part A Visit 12 (Week 24)	Part A+B Study Day 168	154 - < 196	42	

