	Part A Visit 13 (Week 32)	Part A+B Study Day 224	196 - < 252	56	
	Part A Visit 14 (Week 40)	Part A+B Study Day 280	252 - < 308	56	
	Part A Visit 15 (Week 48)	Part A+B Study Day 336	308 - < 378	70	
	Part A Visit 16 (Week 60)	Part A+B Study Day 420	378 - < 462	84	
	Part A Visit 17 (Week 72)	Part A+B Study Day 504	462 - < 546	84	
	Subjects who had assessments at Part A Visit 16/17 are included in safety summaries but not efficacy summaries.				
	Part B Baseline (Day 1)	Date of First 1080 mg Dose = Part B Study Day 1	≤ Part B Study Day 1*	NA	
	Part B Transition Visit 1 (Day 7)	Part B Study Day 7	> Part B Study Day 3 - < Part B Study Day 11	7	
	Part B Transition Visit 2 (Week 2)	Part B Study Day 14	Part B Study Day 11 - < Part B Study Day 21	10	
	Part B Transition Visit 3 (Week 4)	Part B Study Day 28	Part B Study Day 21 - < Part B Study Day 56	25	
	Part B Visit 1 (Week 12)	Part B Study Day 84	Part B Study Day 56 - Part B Study Day < 126	70	
	Part B Visit 2 (Week 24)	Part B Study Day 168	Part B Study Day 126 - Part B Study Day < 210	84	
	Part B Visit 3 (Week 36)	Part B Study Day 252	Part B Study Day 210 - Part B Study Day < 294	84	
	Part B Visit 4 (Week 48)	Part B Study Day 336	Part B Study Day 294 - Part B Study Day < 378	84	
	Part B Visit 5 (Week 60)	Part B Study Day 420	Part B Study Day 378 - Part B Study Day < 462	84	
	Part B Visit 6 (Week 72)	Part B Study Day 504	Part B Study Day 462 - Part B Study Day < 546	84	

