# Apellis Pharmaceuticals, Inc.

PIOLOCOL APL2-CP-AIHA-208	
Part B Long Term Extension Statistical Analysis Plan	

Part	Study Visit	Target Day	Analysis Window	Interval
	Part B Visit 9 (Week 108)	Part B Study Day 756	Part B Study Day 714 - Part B Study Day < 798	84
Part B, cont.	Part B Visit 10 (Week 120)	Part B Study Day 840	Part B Study Day 798 - Part B Study Day < 882	84
	Part B Visit 11 (Week 132)	Part B Study Day 924	Part B Study Day 882 - Part B Study Day < 966	84
	Part B Visit 12 (Week 144)	Part B Study Day 1008	Part B Study Day 996 - Part B Study Day < 1050	84
	Part B Visit 13 (Week 156)	Part B Study Day 1092	Part B Study Day 1050 - Part B Study Day < 1134	84
	Part B Visit 14 (Week 168)	Part B Study Day 1176	Part B Study Day 1134 - Part B Study Day < 1218	84

Version 1.0

08 Nov 2022

\*For baseline assessments, must be prior to dosing.

For the purposes of the all safety and efficacy summary tables and figures by visit, there will be one result per subject per parameter per planned visit per baseline type (Part A + B Baseline and Part B Baseline). The result will be selected in the following priority within each planned subject, visit, parameter, and baseline type:

- Ensure there is an evaluable result (i.e. do not prioritize a NOT DONE assessment)
- Select the date closest to the midpoint of the analysis window per the windowing rules in Section 4.2.3
- 3) For laboratory parameters with central and local labs on the same date, if there is the same date with both local and central lab results, the central lab result is selected

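### Part B SAP visit windows: Visit 12 starts at Day 996 where the SAP's own rule gives 966, two record-selection rules conflict, and no cut-off at the first 1080 mg dose is written into the windowing rules

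*SAP*

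**What the plan says.** All references are to the Part B SAP (08 Nov 2022) unless stated.

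- **Window bounds.** Section 4.2.3 says that "the lower and the upper bound for the analysis visit windows are defined as the midpoints of the target date of the scheduled visits", and that a middle day goes to the later visit. Tables 1 and 2 print Part B Visit 11 (target Day 924) as "Part B Study Day 882 - Part B Study Day < 966" and Part B Visit 12 (target Day 1008) as "Part B Study Day 996 - Part B Study Day < 1050", each with interval 84. Transition Visit 3 is printed as "Part B Study Day 21 - < Part B Study Day 56" with interval 25.
- **Choice among records.** Section 4.2.3 says that "the record closest to the midpoint of the interval will be used in the analysis". Shortly after, it says that "the assessment closest to the target day with non-missing data will be considered for analysis". The numbered list after Table 2 ranks the step "Select the date closest to the midpoint of the analysis window per the windowing rules in Section 4.2.3".
- **Part A and Part B.** Section 2 defines Part A as "the study period of the daily 270/280 mg or 360 mg APL-2 dose regimen". Section 4.2.1 starts Part B on the date of the first 1080 mg dose. Section 5.3.4.3 summarises results up to Part A Visit 15 and then from Part B Baseline. The Part A Visit 15 row of Table 1 (target 336, window 308 to <378) carries no condition tied to that dose. Section 3.3 plans the dose at Visit 15, with transition visits 1, 2 and 4 weeks later.
- **Anaemia classes.** As extracted, section 5.1.3 prints Moderate as 5 to below 10 and Severe as below 8.

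**The concern.** Visit windows decide which record represents a visit in every by-visit table and figure. Three things in 4.2.3 leave that unclear.

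1. The tables contain a hole that the text rule does not allow. The text and the tables therefore tell a programmer different things about a record on Part B Days 966 to 995.
2. Two selection rules sit in one paragraph. They agree only where a window is centred on its target day.
3. The off-centre Part A Visit 15 window extends well past the planned switch of regimen. If the implied end of Part A is not programmed, the Week 48 row could show a value taken on the new regimen. The Part A SAP (27 Apr 2020) had a Visit 15 window centred on Day 336, and its section 4.5 stops rollover data at Visit 15, so interim and final Week 48 values could then differ.

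**Working it through.** **Step 1. Reproduce the printed bounds.** Lower bound = (previous target + own target)/2.

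- Visit 11: (840 + 924)/2 = 882, as printed.
- Visit 12: (924 + 1008)/2 = 966, printed 996.
- Visit 13: (1008 + 1092)/2 = 1050, as printed.

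The rule reproduces every testable Part B bound from Transition Visit 1 to Visit 14 except this one. Width as printed: 1050 − 996 = 54, against a stated 84. Width with 966: 1050 − 966 = 84. Days in no window: 995 − 966 + 1 = 30. For Transition Visit 3, 56 − 21 = 35, not 25; no rule uses that column.

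**Step 2. Which records reach the gap.** The Part B visit tolerance is not in the supplied text. Assuming Part A's ±7 days, Visit 11 falls on 917–931 and Visit 12 on 1001–1015, both outside the gap. It catches a Visit 11 at least 966 − 924 = 42 days late, a Visit 12 at least 1008 − 995 = 13 days early, and unscheduled or early-termination records.

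**Step 3. Where the selection rules differ.** The midpoint is either (low + last day)/2 or (low + upper bound)/2, so each is shown as a range.

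| Window | Target | Midpoint | Difference (days) |
|---|---|---|---|
| Part A Visit 6 (11 to <21) | 14 | 15.5–16 | 1.5–2 |
| Part A Visit 7 (21 to <42) | 28 | 31–31.5 | 3–3.5 |
| Part A Visit 12 (154 to <196) | 168 | 174.5–175 | 6.5–7 |
| Part A Visit 15 (308 to <378) | 336 | 342.5–343 | 6.5–7 |
| Transition Visit 2 (11 to <21) | 14 | 15.5–16 | 1.5–2 |
| Transition Visit 3 (21 to <56) | 28 | 38–38.5 | 10–10.5 |
| Part B Visit 1 (56 to <126) | 84 | 90.5–91 | 6.5–7 |

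That is 7 of the 30 multi-day post-baseline windows in Table 1. Part B Visit 12 as printed would be an eighth (midpoint 1022.5–1023 against 1008); with 966 it is within 0.5 day. The other windows are also within 0.5 day.

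**Step 4. The Visit 15 row, read literally.** Take a first 1080 mg dose on Day 336. Transition Visit 1 (Part B Day 7) is then Day 336 + 6 = 342, inside 308 to <378. It lies 0.5–1 day from the midpoint; the pre-switch Day 336 record lies 6.5–7 days away. The midpoint rule picks Day 342 and the target-day rule picks Day 336. This applies only to parameters collected at transition visits, and that schedule is not in the supplied text.

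**Step 5. Later switchers, read literally.** For a switch at the next 12-week visit (336 + 84 = Day 420), transition visits fall on Days 426, 433 and 447. They miss the Visit 15 window but lie in the Part A Visit 16 window (378 to <462). Part B Visit 1 falls on 420 + 83 = Day 503, in the Visit 17 window (462 to <546). A note in Table 1 keeps Visits 16 and 17 out of efficacy summaries, so these rows concern safety summaries.

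**Step 6. Anaemia classes.** As extracted, a hemoglobin from 5 to below 8 satisfies both Moderate and Severe.

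**The case against.** The strongest reply has four parts.

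- **The text already settles 966.** Section 4.2.3 defines the bounds as midpoints and assigns all post-baseline records to a visit. That identifies the correct figure, but the same section tells the programmer to assign visits from the table, and both tables print 996. The correction is still needed.
- **The numbered list is the operative algorithm, and it names the midpoint.** This largely stands: the target-day sentence may be leftover text, and deleting it would also end the conflict. But the list refers back to the rules of 4.2.3, which contain both. Preferring the target day is a judgement, based on the off-centre windows in Step 3.
- **A cut-off is implied.** Sections 2, 4.2.1 and 5.3.4.3 all point to one. Table 1 also makes little sense without it: for a Day 336 switcher, Part B Visit 1 falls on Day 419, inside the Part A Visit 16 window, and would hold two labels. This stands. A reader might infer from Step 4 that the final tables do show post-switch values at Week 48; the documents do not support that. They show only that the windowing rules do not state the cut-off.
- **The Visit 15 example depends on Table 1's own targets.** The bound of 378 follows from a Visit 16 target of 420. The protocol flow chart and the Part A SAP put Visit 16 at Day 378, which would give (336 + 378)/2 = 357 and a midpoint of 332–332.5. Day 336 would then win under either rule. The example therefore belongs to Table 1 as printed.

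**Conclusion.** Minor, and confined to descriptive summaries, since section 4.3 plans no inferential analysis.

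- **Visit 12:** a confirmed error. It is printed in both tables and contradicted by three other statements in the same SAP, so a reading error in extraction is unlikely. It leaves 30 days unassigned; on-schedule visits miss them under the assumed ±7 days.
- **Selection rules:** a confirmed conflict of wording, with an effect in 7 windows after the 966 correction, and only where a subject has more than one record in the window.
- **Cut-off:** an ambiguity to close. If the literal reading were programmed for a Visit 15 switcher, the pre-switch value would still appear as Part B Baseline, so it would be mislabelled rather than lost. It would also be too strong to say that later switchers are untouched: that holds for the Visit 15 row only.
- **Anaemia classes:** a query only. The overlap rests on one digit printed once in extracted text, so the documents do not establish that the plan's classes are wrong.

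The number of subjects affected by any of these cannot be derived from the documents.

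**What to change.** 1. Change 996 to 966 in Tables 1 and 2. As a cosmetic correction, change the Transition Visit 3 interval from 25 to 35.
2. Keep one selection rule in both the 4.2.3 text and the numbered list. Closest to target day is the better choice; the tie-break should then refer to the target day as well. The Part A SAP (section 4.1.2) contains the same two rules, so establish which one the interim analysis used and note any difference in the report.
3. Add one sentence: records after the first 1080 mg dose are not eligible for any Part A window. Apply the single selection rule to the records that remain. Do not add a separate rule that the last pre-dose record serves as Visit 15. With an unscheduled record on Day 336 and a pre-dose record on a Day 340 switch, that rule would pick 340 and the target-day rule 336, which brings back two competing rules.
4. Ask the sponsor to check the anaemia class limits in section 5.1.3 against the source and reconcile them if the overlap is real.

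The cost is one figure in two tables, one printed interval, a few lines of text and trivial reprogramming.

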# Apellis Pharmaceuticals, Inc.

PIOLOCOL APL2-CP-AIHA-208	
Part B Long Term Extension Statistical Analysis Plan	

Part	Study Visit	Target Day	Analysis Window	Interval
	Part B Visit 9 (Week 108)	Part B Study Day 756	Part B Study Day 714 - Part B Study Day < 798	84
Part B, cont.	Part B Visit 10 (Week 120)	Part B Study Day 840	Part B Study Day 798 - Part B Study Day < 882	84
	Part B Visit 11 (Week 132)	Part B Study Day 924	Part B Study Day 882 - Part B Study Day < 966	84
	Part B Visit 12 (Week 144)	Part B Study Day 1008	Part B Study Day 996 - Part B Study Day < 1050	84
	Part B Visit 13 (Week 156)	Part B Study Day 1092	Part B Study Day 1050 - Part B Study Day < 1134	84
	Part B Visit 14 (Week 168)	Part B Study Day 1176	Part B Study Day 1134 - Part B Study Day < 1218	84

Version 1.0

08 Nov 2022

\*For baseline assessments, must be prior to dosing.

For the purposes of the all safety and efficacy summary tables and figures by visit, there will be one result per subject per parameter per planned visit per baseline type (Part A + B Baseline and Part B Baseline). The result will be selected in the following priority within each planned subject, visit, parameter, and baseline type:

- Ensure there is an evaluable result (i.e. do not prioritize a NOT DONE assessment)
- Select the date closest to the midpoint of the analysis window per the windowing rules in Section 4.2.3
- 3) For laboratory parameters with central and local labs on the same date, if there is the same date with both local and central lab results, the central lab result is selected

### 4.3 Test Hypothesis and P-Value Justification

No formal inferential statistics will be applied to data collected in this study.

### 4.4 Procedures for Handling Missing Data and Dropouts

A missed visit and assessment details eCRF page will summarize which visits / assessments were missed along with the reason (e.g., COVID-19, or other). This will be listed for both Part A + B and Part B.

Version 1.0

#### 4.4.1 Safety Data

Where appropriate, screening values may be used as baseline in the event of missing or unusable Day 1 measurements. No imputation of missing data for early terminations will be performed.

However, both partial and completely missing dates/times that are not related to early terminations, in addition to missing safety data (e.g., missing severities) will be reviewed on a case-by-case basis for potential imputations. As a general rule, a conservative approach will be adopted as outlined in Section 5.2.1 (e.g. partial Adverse Event (AE) onset dates and missing severities will be taken as the earliest 'on treatment' start date and highest severity, respectively, consistent with the partial information available). Moreover, the original data, without imputations, will be presented separately in data listings.

For safety lab parameters that are below or above the limit of quantification, the data will be presented as-is in the listings, but the limit of quantification will be used for the purposes of calculating change from baseline.

### 4.4.2 PK and Efficacy/PD Concentration Data

APL-2 concentrations reported from pre-dose on Day 1 to the time of the first quantifiable value will be taken as zero for linear plots and the calculation of PK parameters, and equal to the lower limit of quantification (LLOQ) for semi-logarithmic plots.

After this time point, concentrations below the limit of quantification (BLQ) will be set to zero, with the exception of the calculation of the geometric mean where the LLOQ will be used.

If a BLQ value falls between two quantifiable concentrations the value will be set equal to the LLOQ, unless its exclusion can be justified (e.g. implausibility given the profile observed and known PK properties). In the event of a missing PD baseline value a screen measurement or pre-dose unscheduled measurement may be used (whichever is closer to the baseline date).

If a baseline PD value is zero, then the percent change from baseline will not be calculated. If a post baseline value is BLQ, then the value will be set to the LLOQ. Similarly, for PD plots, a BLQ value will be set equal to LLOQ.

## 4.5 Subgroup Analysis

Due to the small sample size of the study, no subgroup analyses will occur.

#### 4.6 Multi-Center Studies and Pooling of Centers

This is a multi-center study. Due to the small number of subjects at each site, no adjustments will be made for study site.

Apellis Pharmaceuticals, Inc.	
Protocol: APL2-CP-AIHA-208	
Part B Long Term Extension Statistical Analysis Plan	Version 1.0

# 5. STATISTICAL ANALYSIS METHODOLOGY

In general, tables will be presented by cohort (Cohort 1 wAIHA / Cohort 2 CAD) and study part (Part A + B / Part B). The Part B summaries will start from Study Day 1 in Part B through the end of the Part B Long Term Extension Phase, while Part A + B will start from Study Day 1 in Part A through the end of the Part B Long Term Extension Phase.

Tabulations for continuous data will use a standard set of descriptive statistics for the results and for change from baseline, as specified: number of observations available (n), mean, standard deviation (SD), median, and range (minimum, maximum). Change from Baseline for Part A + B summaries will calculate the Change from Part A Baseline summary statistics. Change from Baseline for Part B summaries will calculate the Change from Part B Baseline summary statistics.

Categorical or dichotomous data will be tabulated using frequencies (counts and percentages). The numerator and denominator for each percentage calculation will be specified in the footnotes of table shells. Categorical data will be populated as appropriate for each study part (Part A + B and Part B).

Data listings will present all information recorded in eCRFs for all subjects and visits. All listings will be sorted by cohort and subject number.

